### 10.7.8 Prior and concomitant therapy

Adjuvant chemotherapy or other therapy that are considered necessary for the patient's welfare may be given at the discretion of the Investigator.

Post operative treatment with low dose heparin must be withdrawn before administration of study treatment.

Administration of IMP will be temporary discontinued during enterostomy closure or any other procedure requiring administration of low molecular weight heparin. The IMP will be stopped the day before administration of the low molecular weight heparin. The IMP will be administered again the day after the treatment with low molecular weight heparin has stopped. The temporary discontinuation of IMP cannot be longer than 30 days.

In patients receiving adjuvant chemotherapy and that have a drop in their platelets count ( $<100 \times 10^9/L$ ) due to this, administration of IMP can be temporary discontinued until the chemotherapy treatment stops. The IMP will be administered again as soon as platelets are over  $\geq 100 \times 10^9/L$ .

Patients with regular administration of ASA defined as  $>3$  doses /week will be included in observation group. Other additional regular use of ASA must be withdrawn before randomization.

All concomitant therapy used during the trial period must be recorded in the eCRF. Adjuvant chemotherapy administrated prior to the trial period will also be documented.

No other drug under investigation may be used concomitantly with the trial medication.

### 10.7.9 Treatment compliance

Treatment compliance will be made by medication count by the study personnel at the site.

## 10.8 Trial assessments

The following will be assessed during the study.

### 10.8.1 Demographic and baseline characteristics

- Demographics such as gender and age will be recorded.
- Karnofsky status will be assessed by the Investigator according to the following;
  - 100%, normal no complaints, no evidence of disease
  - 90% able to carry on normal activity, minor signs or symptoms of disease
  - 80% normal activity with effort, some signs or symptoms of disease
  - 70% cares for self, unable to carry on normal activity or to do active work

- 60% require occasional assistance, but is able to care for most of their personal needs
- All relevant medical and surgical history within the last 3 years must be documented in the eCRF.
- A colonoscopy or CT colon performed within 3 months from surgery demonstrating a clean colon i.e. no tumors available apart from the tumor that will be removed during surgery.
- A distant recurrence investigation according to local practice available within 3 months before surgery will be collected.

#### 10.8.2 Molecular profiling of the tumors

Patients with stage I-III will be included in the screening process preoperatively or short after surgery. The pathology result will classify the tumor and patients with tumor stage II-III and colon cancer or tumor stage I-III and rectal cancer will be randomized. Patients with clinical tumor stage IV will be excluded before screening Part 1.

From all patients that are pre- or postoperatively eligible to be included in the ALASCCA study, a standardised piece (approximately 10x20x5 mm) is routinely cut from the primary tumor and fixated in formalin at the local pathology department. At the regional or local pathology department, this piece is sectioned, stained and the tumor content in the selected piece is estimated. This selected tumour piece is then sent to the selected laboratory of choice.

The following somatic alterations in the tumours are defined as inclusion criteria in the ALASCCA study:

- Somatic mutations affecting the function of the *PIK3CA*, *PIK3R1* or *PTEN* genes
- Homozygous deletion of the *PTEN* gene

In addition, mutation analysis of the *BRAF*, *KRAS* and *NRAS* genes and Mismatch Repair (MMR) status (Microsatellite instability, MSI, alt Immunohistochemistry, IHC, for MMR genes) are also performed on the selected tumour piece/sections and forwarded back to both the treating doctor and to the local pathology lab. These genomic alterations are already used in clinical routine today and will add value to the clinic.

The molecular analyses can either be performed at a regional pathology department or at the national reference laboratory at Science for Life Laboratory in Stockholm.

#### 10.8.3 Laboratory measurements

If CEA and platelets are not available according to normal praxis, the samples will be taken. The handling of the samples will be made according to the routines at each site. Analysis will be made by the local lab at the sites.

- CEA- 3.5 ml (serum) will be taken for analysis of CEA.
- Platelets- 4 ml (EDTA) ml blood sample will be taken for analysis of platelets.
- A urine pregnancy test- will be taken on all female patients with child-bearing potential unless they

- have undergone surgical sterilization
- are post menopausal

The pregnancy test will be a commercially available urine test.

- A 4 ml (EDTA) blood sample is sent directly to Karolinska Institutet Biobank for extraction of germline DNA to be used for the molecular profiling.
- Plasma- 2 x 4 ml (EDTA) blood will be taken for biobank storage for any future analysis.

#### 10.8.4 Efficacy assessments

##### Primary clinical efficacy assessments

The primary clinical efficacy assessment will be CT thorax and abdomen. The CT will be performed, year 1 and 3 during the treatment phase.

##### Secondary clinical efficacy assessments

OS will be reviewed during the study. In case the patient dies during the study the cause of death will be recorded.

Time until relapse will also be documented.

#### 10.8.5 Safety assessments

The safety assessment will include AEs. Especially focus will be on bleeding complications.

#### 10.8.6 Safety Monitoring committee

An independent Safety Monitoring Committee will be responsible for evaluation of safety. The committee will consist of independent physicians. A separate document will be written describing the process in details

#### 10.8.7 Adverse Events (AEs)

##### 10.8.7.1 Definitions

###### **Adverse Event**

Any untoward medical occurrence in a patient or clinical trial patient administered a medicinal product and which does not necessarily have to have a causal relationship with this treatment. An AE can therefore be any unfavourable and unintended sign (e.g. an abnormal laboratory finding), symptom, or disease temporally associated with the use of an IMP, whether or not considered related to the IMP.

###### **Serious Adverse Event (SAE)**

An SAE is any untoward medical occurrence or event, at any dose, that:

- results in death
  - is life threatening
  - requires hospitalization or prolongation of existing hospitalization
  - results in persistent or significant disability/incapacity
  - is a congenital anomaly/birth defect.
- or
- other important medical event (example of such events are convulsions that do not result in hospitalization)

Medical and scientific judgment should be exercised in deciding whether expedited reporting is appropriate in other situations, such as important medical events that may not be immediately life-threatening or result in death or hospitalization but may jeopardize the patient's health or may require intervention to prevent one of the other outcomes listed in the definitions above. These AEs should also usually be considered as *serious*.

#### **Suspected Unexpected Serious Adverse Reaction (SUSAR)**

A SUSAR is a **suspected unexpected serious adverse reaction**, potentially causally related to the investigational medicinal product, and will be reported to the appropriate IEC and RA.

#### 10.8.7.2 Eliciting and recording of AEs

The method for collecting and recording AEs will be spontaneous reporting and open question e.g. "How have you felt since previous visit" during the treatment and follow-up period.

All AEs, serious and non-serious, and pre-existing conditions, should be recorded in the eCRFs. If no AE has occurred during the trial period, this should also be recorded.

#### Exception

Events directly connected to expected chemotherapeutics side effects e.g. nausea, diarrhoea neutropenia and infections related to neutropenia will not be reported as AEs.

Planned enterostomy closure performed after administration of IMP and complications after the closure will not be reported as AE/SAE.

In case of any bleeding events related to the above, the event should be reported as an AE/SAE.

The following evaluations are to be done by the Investigator in connection with the AE:

- *description of the AE*
  - If possible the Investigator uses the diagnosis for description of the event. If not the diagnosis is decided, report the primary sign or symptom as the AE or SAE term
- *seriousness*
  - Yes or No, see definition of a SAE for seriousness, as of above.
- *intensity*
  - Mild - Symptoms which are easily tolerated (acceptable)

- Moderate - Symptoms which interfere with usual activity (disturbing)
- Severe - Symptoms which give incapacity to do usual activity (unacceptable)

If the intensity changes during the period of the AE the maximum intensity should be recorded.

- *duration of the AE (start - end)*
- *action taken due to the AE*
  - None
  - IMP stopped
- *causality rating with investigational medicinal product*
  - Not related: Indicates that the AE is definitely not related to the study drug.
  - Related: .
    - The AE could have been produced by the patient's clinical status or the medicinal product.
    - The AE follows a reasonable temporal sequence from the time of administration of the medicinal product, and can not be reasonably explained by the known characteristics of the patient's clinical status.
- *outcome of the AE*
  - Recovered/Resolved
  - Recovering/Resolving
  - Not recovered/Not resolved
  - Recovered/Resolved with sequelae
  - Fatal
  - Unknown

#### 10.8.7.3 Pre-existing condition:

Events available at the first administration of IMP are part of baseline information (pre-existing conditions). These events will be considered as AE, only if they worsen after first administration of IMP.

Elective procedures or surgery planned before first administration of IMP is not considered as an AE/SAE.

#### 10.8.7.4 Reporting of SAEs

All SAEs must be reported by the Investigator using phone, mail or fax within 24 hours from the Investigator's knowledge of the event to the Monitor or other members of the staff at the Sponsor, regardless of the time that may have elapsed from the time the event occurred to when the Investigator first learns of it. The initial report should contain as a minimum the following information:

- 
- patient identification
  - treatment specification
  - diagnosis or symptoms
  - time specification for the SAE
  - name of the original reporter

A SAE report form must also be completed, signed by the Investigator and submitted to the monitor or the Sponsor no later than five working days after the initial information was received. Apart from the information above, this follow-up report should also contain the following information:

- assessment of intensity
- assessment of causality

No distinction should be made between the tested investigational product and the reference/comparator product regarding reporting of SAEs as long as the code is not broken.

Only SAEs that are both unexpected and assessed as related to IMP(s), i.e. SUSARs, are patient to expedited reporting to the appropriate IEC and RA, by the Sponsor.

#### 10.8.7.5 Follow-up of unresolved AEs

If a patient is withdrawn due to an AE, or if an AE persists at the end of the trial treatment period, this should be followed up until the condition has ceased or until the patient is under professional medical care and a potential causality between IMP and the AE has been penetrated. An outcome assessment should be performed when an AE persists.

#### 10.8.7.6 Procedures in case of pregnancy

In case of pregnancy or suspicion of possible pregnancy, the trial treatment must be stopped immediately, and the patient discontinued from participation in the trial. Pregnancy itself is not regarded as an AE unless there is a suspicion that the IMP may have interfered with the effectiveness of the contraceptive medication. However, the outcome of all pregnancies (spontaneous miscarriage, elective termination, normal birth or congenital abnormality) must be followed up and documented even after the patient was discontinued from the trial.

All events of congenital abnormalities/birth defects are SAEs. Spontaneous miscarriages should also be reported and handled as SAEs. All outcomes of pregnancy must be reported to the Sponsor on the pregnancy report forms; Part I (at confirmed pregnancy) and Part II (pregnancy outcome).

#### 10.8.7.7 Coding of AEs

All AEs will be coded according to Medical Dictionary for Regulatory Activities (MedDRA). All SAEs are coded upon reporting to the Sponsor. The coding will be performed by the Sponsor.

## 10.9 Data Management

Data from the study will be collected from the medical records and from the Swedish Colorectal Cancer Registry (SCRCR). Part of the information from the medical records will be entered into eCRF e.g. date of visits, study treatment, concomitant medication and AEs. Other parts will be imported to the study data base from the SCRCR e.g. tumor characteristics, surgical procedure, adjuvant treatment and long term follow-up.

Other external data e.g. laboratory data will be entered or transferred into the study database.

### **10.10 Swedish Colorectal Cancer Registry (SCRCR)**

Patients included in the study are also part of the SCRCR. The register was launched in 1995 for rectal cancer and since 2007 it also includes patients with colon cancer. The database is continuously validated and updated and >98 % of the patients are included in the register. The SCRCR contains information such as patient demographics, (neo) adjuvant treatment, surgical procedure, tumor characteristics and short and long term follow-up.

### **10.11 Quality Control**

A quality control (QC) of data will be performed to ensure that data entry and verification have been performed correctly in accordance to pre-defined instructions. The QC will be performed as described in the Data Management Plan. The QC will be performed before data is declared clean.

### **10.12 Data Quality Assurance**

#### **10.12.1 Case Report Forms (eCRFs)**

The Monitors will review and verify the data collected in the eCRFs and SCRCR against the source documents during monitoring visits. The Monitors will address the discrepancies found in the data and will ensure that corrections to the data are properly made and documented by the site personnel. All corrections will be documented in an audit trail.

#### **10.12.2 Monitoring**

The trial site will be visited by the Monitor and/or the Clinical Trial Manager (co-monitoring) periodically at times agreed with the Investigator. It is the function of the Monitor to ascertain that all aspects of the protocol are complied with and that the conduct of the trial conforms to applicable regulatory requirements and established rules for Good Clinical Practice (GCP).

Preferably at the time of each monitoring visit, the Monitor will

- review the completed eCRFs to ascertain that items have been completed and that the data provided are accurate and obtained in the manner specified in the protocol.
- verify that the data in the eCRF and SCRCR register are consistent with the clinical records or other relevant record (Source Data Verification) and that trial results are recorded completely and correctly.

- verify compliance with the procedures for reporting of SAEs, product accountability and record keeping.

For this purpose the Monitor must be given direct access to clinical records, original laboratory data, etc., as far as these relate to the trial and without jeopardizing patient integrity. The Investigator and other relevant personnel should be available during the monitoring visit and should devote sufficient time.

#### 10.12.3 Training of staff

All Investigators and staff carrying out observations of primary or other major efficacy variables involved in the trial should provide a curriculum vitae. The Investigator will keep a list of all personnel involved in the trial together with their function and trial related duties delegated. He/she will ensure that appropriate trial related training is given to all of these staff, and that any new information of relevance to the performance of this trial is forwarded to the staff involved.

Before inclusion of patients the Monitor will perform a trial initiation visit to inform and train relevant trial staff.

#### 10.12.4 Audit and inspections

The trial site may be patient to quality assurance audit by the Sponsor or someone appointed for this task by the Sponsor. A RA may request to make an inspection of the trial site. The procedures of such a visit would be similar to those of a monitoring visit, and data already checked by the Monitor may be checked again. The Investigator is required to inform the Sponsor immediately of an inspection requested by a RA. The Investigator and other relevant personnel must be available during the audit/inspection and must devote sufficient time.

#### 10.12.5 Changes in the approved Trial Protocol

Trial procedures must not be changed without the mutual agreement of the Investigator and the Sponsor.

Any substantial change to the approved Final Trial Protocol will be documented in a written and numbered Protocol Amendment. Any proposed substantial change to the Final Trial Protocol must be discussed with and approved by the Sponsor before submitted to IEC and Regulatory Authority for approval, according to applicable national regulations.

### **10.13 Statistical methods and determination of sample size**

The statistical analysis will be described in detail in the Statistical Analysis Plan including a Data Display Plan, which will be in a final draft version prior to study start and finalized and approved before database lock.

The primary statistical analysis will be done at 3 years of study treatment and an analysis of overall survival (OS) will be done at 5 years.

### 10.13.1 Demographics and baseline data

All data will be presented using descriptive statistics. Results will be presented in total and by treatment group. Continuous variables will be summarized using mean, standard deviation, median, minimum and maximum. Categorical variables will be summarized using the number and percentage of patients.

### 10.13.2 Endpoints

#### 10.13.2.1 Primary Endpoint

Primary endpoint TTR at 3 years will be analyzed in patients with tumors harboring *PIK3CA* mutations in exon 9 and 20.

TTR is defined as time from randomization to occurrence of any of the following; loco-regional recurrence, distant metastases or death from colorectal cancer.

#### 10.13.2.2 Secondary Endpoint

Secondary endpoint DFS at 3 years will be analyzed in patients with tumors harboring *PIK3CA* mutations in exon 9 and 20.

DFS and TTR at 3 years will be analyzed in patients with tumors harboring *PIK3CA* mutations other than in exon 9 and 20 and in *PIK3R1* and *PTEN*.

DFS is defined as time from randomization to occurrence of any of the following events; loco-regional recurrence, distant metastases, second primary colorectal cancer, second primary other cancer, death from colorectal cancer, death from other cancer, non-cancer related death and treatment-related death whichever comes first.

OS at 5 years will be analyzed in patients receiving low-dose ASA versus placebo.

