#### Secondary Endpoints

- DFS at 3 years, in patients with tumors harboring *PIK3CA* mutations in exon 9 and 20.
- DFS at 3 years, in patients with tumors harboring *PIK3CA* mutations other than in exon 9 and 20 and in *PIK3R1* and *PTEN*.
- TTR at 3 years, in patients with tumors harboring *PIK3CA* mutations other than in exon 9 and 20 and in *PIK3R1* and *PTEN*.
- OS at 5 years, in patients with tumors harboring *PIK3CA* mutations in exon 9 and 20, other than in exon 9 and 20 and in *PIK3R1* and *PTEN*.

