		
In addition to the items that will be performed during the treatments visits, the following will be performed at the time of visit 7 and 15 (after 1 and 3 years);
 
 
• CT/MRI (Magnetic Resonance Imaging) thorax and abdomen
 
• CEA (Optional)
 
 
The following assessments will be performed during the follow-up visit;
 
 
• Documentation of CEA (Optional), if not available a sample will be taken
 
• Review if there is any clinical suspicion of recurrence
 
 
Page 26: CEA (Optional)

5.2	25 Jan 2021	The total number of patients to be included is changed from 816 to 600 (300 in group A and 300 in group B) and the study time table is changed.

3	TABLE OF CONTENTS	
1	PROTOCOL SYNOPSIS	2
	Inclusion criteria	4
	Exclusion criteria	4
2	REVISION HISTORY	7
3	TABLE OF CONTENTS	9
4	PROTOCOL SIGNATURE PAGE	12
5	INVESTIGATOR SIGNATURE PAGE	13
6	LIST OF ABBREVIATIONS AND DEFINITION OF TERMS	14
7	ETHICS	15
7.1	Ethical and Regulatory review	15
7.2	Ethical conduct of the trial	15
7.3	Patient information and consent	15
7.4	Patient data protection	15
8	INVESTIGATOR(S) AND TRIAL ADMINISTRATIVE STRUCTURE	16
9	INTRODUCTION	17
10	TRIAL OBJECTIVES AND ENDPOINTS	19
10.1	Primary objective	19
10.2	Primary endpoint	19
10.3	Secondary objective	19
10.4	Secondary endpoint	19
10.5	Exploratory objectives	20
10.6	Safety Endpoints	20
11	INVESTIGATIONAL PLAN	20
11.1	Overall trial design	20
11.2	Study procedures	22
11.2.1	Screening (Visit 1)	22
11.2.2	Randomization (Visit 3)	23
11.2.3	Phone calls (Visit 4, 6, 8, 10, 12 and 14)	23
11.2.4	Treatment visits (Visit 5, 7, 9, 11, 13, 15)	23
11.2.5	Follow-up period (Final visit 16)	24
11.3	Observation group	24
11.4	Rationale for trial design, doses and control group	27

11.5	Risk/benefit assessment.....	27
11.6	Selection of trial population .....	27
11.6.1	Inclusion criteria.....	28
11.6.2	Exclusion criteria.....	28
11.6.3	Patients treated with ASA before randomization.....	29
11.6.4	Removal of trial patients from treatment or assessments.....	29
11.7	Treatments .....	30

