### 9.3 Secondary objective

- To determine whether adjuvant treatment with 160 mg ASA once daily for 3 years can improve Disease-Free Survival (DFS) in patients with colorectal cancer with somatic alterations in the *PIK3CA* (exon 9 and 20) compared with placebo.
- To determine whether adjuvant treatment with 160 mg ASA once daily for 3 years can improve DFS in patients with colorectal cancer with somatic alterations in the *PIK3CA* (other than exon 9 and 20), *PIK3R1* or *PTEN* genes compared with placebo.
- To determine whether adjuvant treatment with 160 mg ASA once daily for 3 years can improve TTR in patients with colorectal cancer with somatic alterations in the *PIK3CA* (other than exon 9 and 20), *PIK3R1* or *PTEN* genes compared with placebo
- To compare overall survival (OS) at 5 years from randomization in patients receiving low-dose ASA versus placebo.
- To assess overall safety and tolerability.

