# 10 INVESTIGATIONAL PLAN

## 10.1 Overall trial design

ALASCCA is a randomized, parallel group, double blind, multicenter, placebo-controlled, biomarker-based study of adjuvant treatment with ASA in colorectal cancer. The study will compare DFS, time to relapse and OS and will assess safety and tolerability.

Patients (adult male and female) with colorectal cancer clinical stage I-III with localized disease are considered for the study. Patients will be screened for inclusion at the time of surgery of the tumor (at time of routine patient visit before elective surgery or postoperatively within 12 weeks in case of emergency procedure or if screening was missed preoperatively). After inclusion and when surgery is performed, patients with *PIK3* mutations and colon cancer stage II and III tumors or rectal cancer stage I-III, will be randomized to receive 160 mg ASA or placebo orally. Last date for randomization and start of treatment is 12 weeks postoperatively. The treatment can be administered alone or in combination with adjuvant chemotherapy. The choice of any adjuvant chemotherapy is made by the Investigator and should follow the guidelines in the National Care Program ([www.cancercentrum.se](http://www.cancercentrum.se)). The treatment will be administered for 3 years. There will be a follow-up period for two years. Outside the trial, the patient will be treated according to standard care at the site.

A phone contact will be made 3 months after the randomization visit and thereafter every 6th month. The patients will also visit the site 6 months after randomization and thereafter every 6th

month i.e. the patients will be in contact with the site every 3rd month. There will also be a visit/phone contact at the end of the follow-up period.

A total of 3750 patients will be screened in order to include 300 patients with *PIK3CA* (*Exon 9 and 20*) mutated tumors in each treatment arm (Group A). With an estimated 10 % drop-out rate, 150 patients will be randomized in each arm. This also includes approximately 15 % of the patients that will be excluded due to tumor stage 1.

An additional 300 patients with mutations in other PI3K pathway genes *PIK3CA* (other than exon 9 and 20), *PIK3R1* or *PTEN* will also be randomized in each arm and will be treated as a separate group in the analyses (Group B). With an estimated 20 % drop-out rate, 150 patients will be randomized in each arm.

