### 10.7.3 Doses and treatment regimens

The patient will receive IMP in a package covering a period of 6 months+1 week. The patient will receive one package at each treatment visit. One tablet will be administered once daily. The tablet will be swallowed with a glass of water.

The randomized schedule will make sure that 300 patients (150 patients from Group A and Group B) will receive 160 mg ASA and 300 patients (150 patients from Group A and B) will receive a matching placebo tablet.

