4.3.2 Secondary endpoints

- 1. DFS assessed at 3 years from randomization, in subjects with tumors harboring somatic alterations in the PIK3CA (exon 9 and/or 20) gene.
- 2. TTR assessed at 3 years from randomization, in subjects with tumors harboring somatic alterations in the PIK3CA (not exon 9 or 20), PIK3R1 and/or PTEN genes.
- 3. DFS assessed at 3 years from randomization, in subjects with tumors harboring somatic alterations in the PIK3CA (not exon 9 or 20), PIK3R1 and/or PTEN genes.
- 4. OS assessed at 5 years from randomization, in subjects with tumors harboring somatic alterations in the PIK3CA (exon 9 and/or 20) gene.
- 5. OS assessed at 5 years from randomization, in subjects with tumors harboring somatic alterations in the PIK3CA (not exon 9 or 20), PIK3R1 and/or PTEN genes.
- 6. Frequency and severity of adverse events (AE). Cerebral and gastric hemorrhage (for interim analyses).

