8.3 Exploratory analyses

In addition to the primary efficacy analysis and the analyses of secondary endpoints, some or all of the exploratory analyses listed in Table 10 (3-year endpoints) and Table 11 (5-year endpoints) may also be performed. All exploratory endpoints on the FAP will be analyzed as described in Section 8.1, however, for analyses in only colon/rectum/left-sided/right-sided colon subjects, the strata will only be defined by stage. For analyses with subgroups based on adjuvant treatment, an interaction-term between randomization arm and a time-varying treatment indicator will be used considering that adjuvant treatment for some subjects starts post-randomization. In result tables for exploratory analyses, 95 % Cl's, unadjusted for multiple testing will be presented, but not p-values.

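### Combined Mutation A + B Cox models leave out mutation type, a randomisation factor, and the protocol and SAP do not agree clearly on whether 5-year OS is one comparison or two

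*Protocol*

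**What the plan says.** **Strata.** SAP Section 4.6, Table 3, stratifies randomisation by location, stage and mutation type. SAP Section 8.1 stratifies the baseline hazard by the randomisation covariates and lists five strata, all location by stage. That is complete for the primary population, where everyone is Mutation A. SAP Section 8.3 then applies Section 8.1 to all exploratory endpoints in the full analysis population (FAP). The only change is that analyses restricted to a tumour site are stratified by stage alone. These rows of Tables 10 and 11 mix the two mutation groups:

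- TTR and DFS in A + B
- TTR and DFS in A + B with clonal high-confidence drivers
- the four tumour-site rows that name no mutation group
- 5-year TTR and OS in A + B

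**OS in the protocol.** Section 9.3 states the objective as "To compare overall survival (OS) at 5 years from randomization in patients receiving low-dose ASA versus placebo". Section 10.13.2.2 repeats it: "OS at 5 years will be analyzed in patients receiving low-dose ASA versus placebo". Neither names a mutation group, while every DFS and TTR objective does. The endpoint lists (synopsis and Section 9.4) give OS a single bullet that names the groups, beginning "OS at 5 years, in patients with tumors harboring *PIK3CA* mutations in exon 9 and 20, other than in exon 9 and 20". Section 10.1 says of the Group B patients that they "will also be randomized in each arm and will be treated as a separate group in the analyses (Group B".

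**OS in the SAP.** Section 4.3.2 sets secondary endpoint 4 as "OS assessed at 5 years from randomization, in subjects with tumors harboring somatic alterations in the PIK3CA (exon 9 and/or 20) gene" and endpoint 5 as the same for Mutation B. Combined OS is a row of Table 11. Section 8.3 makes "some or all of the exploratory analyses listed in Table 10" and Table 11 optional, reported with 95% CIs but no p-values. Figure 6 in the list of figures is a Kaplan-Meier plot of combined OS.

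**The concern.** The SAP's own principle is to stratify the analysis by what was stratified in the randomisation. It follows that principle for the single-group analyses and drops it, apparently by carry-over, once the groups are combined. A combined model without mutation type puts A and B patients under one baseline hazard. If the two groups differ in prognosis, that costs a little efficiency and pulls the hazard ratio slightly towards 1.

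The OS point is about what will be reported. The protocol's OS objective is unrestricted, but the only OS analyses the SAP commits to are restricted to one group each. If the optional row is not run, no combined hazard ratio would answer the objective as worded, and the SAP does not say why the objective was divided.

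**Working it through.** **1. Strata**

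- Randomisation strata: five location-by-stage cells × 2 mutation types = 10. Analysis strata in Section 8.1: 5.
- In a Mutation A or Mutation B analysis, mutation type is constant, so 5 strata are enough. In an A + B analysis it takes both values, so 5 strata omit it.
- Under SAP Section 4.6 the next subject in a stratum always goes to the smaller arm, so the arms differ by at most 1 per stratum. Taking a stratum as the cross of the three factors, the arms differ by at most 5 within each mutation group of about 300. The omission therefore does not create meaningful confounding. What is lost is some efficiency, and the documents give no prognostic difference between A and B from which to size it.

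**2. The plan's only power figure**

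Neither document gives a power, event rate or effect size for OS. The current calculation is for 3-year TTR in Mutation A (SAP Section 4.5.2): 18% on placebo, RR 0.38, two-sided 5%, 80% power, test of two proportions.

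- p1 = 0.18, p2 = 0.18 × 0.38 = 0.0684, mean 0.1242
- n = [1.96 √(2 × 0.1242 × 0.8758) + 0.842 √(0.18 × 0.82 + 0.0684 × 0.9316)]² / 0.1116² = 136 per arm
- The SAP has 135 per arm before drop-out, where power is 79.7%. Adding drop-out gives 136/0.9 = 152, or 136 × 1.1 = 150; the SAP has 150. The figure reproduces.

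**3. One OS comparison or two: what depends on no OS rate**

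The planned size is 600, with 300 in each group. Protocol Section 10.7.3 gives the allocation: "300 patients (150 patients from Group A and Group B) will receive 160 mg ASA", and the same number placebo. Section 10.1 also mentions 300 in each arm beside 150; I used 150 per arm per group.

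With a common hazard ratio and half the events in each group, the expected z is divided by √2:

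power per group = Φ[(1.96 + z of combined power)/√2 − 1.96]

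| Combined power | Power per group |
|---|---|
| 70% | 42% |
| 80% | 51% |
| 90% | 63% |
| 95% | 72% |

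**4. Illustration with assumed OS inputs**

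Assumptions: 10% drop-out throughout (540 evaluable combined, 270 per group) and placebo 5-year mortality m0 = 20%. Mortality on ASA is m1 = 1 − (1 − m0)^HR, events D = N(m0 + m1)/2, power = Φ(√D/2 × |ln HR| − 1.96).

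| Common HR | Combined D | Combined power | Power per group |
|---|---|---|---|
| 0.5 | 82.5 | 88% | 61% |
| 0.6 | 87.8 | 67% | 40% |
| 0.7 | 93.0 | 41% | 23% |

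Over assumed placebo mortality of 10% to 25%, the hazard ratio detectable with 80% power runs from 0.40 to 0.59 combined and from 0.26 to 0.45 per group. Protocol Section 10.1 allows 20% drop-out in Group B, which would lower the Group B and combined figures slightly.

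**5. Effect confined to Mutation A**

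HR 0.5 in A, 1.0 in B, other inputs as in step 4:

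- A: m1 = 1 − 0.8^0.5 = 0.1056, so D = 270 × 0.3056/2 = 41.25; power 61%.
- B: D = 270 × 0.20 = 54.
- Combined: average ln HR = (41.25/95.25) × ln 0.5 = −0.300 on 95.25 events; power 31%.

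The ordering reverses.

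**The case against.** A reader might infer that the SAP departed from the protocol, dropped the combined OS comparison and gave up much of the trial's OS power. The documents do not support that.

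- **Departure.** Protocol Section 10.1 says Group B is analysed separately and makes no exception for OS. The OS endpoint bullet names the groups and nowhere says they are combined. Two group-specific endpoints are a permissible reading. What stands is that the objective and analysis sentences read more naturally as one comparison, and that the SAP gives no reason for two.
- **Dropped.** Combined OS remains in Table 11 and Figure 6. Protocol Section 10.13.3 plans point estimates and 95% CIs for secondary variables, and Table 11 results would carry both. What is missing is a firm commitment to the hazard ratio, and a p-value.
- **Power.** There is no OS power in the plan to lose. The fall from 80% to about 51% needs a common hazard ratio. Protocol Section 8 calls the role of PIK3R1 and PTEN in the ASA effect unknown, and the primary hypothesis concerns Mutation A alone; step 5 shows that combining dilutes if only A responds. With a common HR of 0.5, the chance that at least one group-specific test succeeds is 1 − (1 − 0.605)² = 84%, against 88% combined. That uses two unadjusted 5% tests, with a family-wise error of 1 − 0.95² = 9.75%, and success in one group alone does not answer an unrestricted objective.

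There is also a timing objection. The 3-year results by group, with DFS that counts deaths, come well before OS. Promoting combined OS after that would change an endpoint's status with relevant data in view. This stands, and limits what should be asked.

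Against the strata point, one can say that these analyses are exploratory and the allocation is already balanced. That is why the gain is small; it is no reason to leave the factor out.

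**Conclusion.** The strata gap is real on either reading of the OS objective. As written, the combined A + B models in the FAP omit one of the three factors the trial randomised by. The effect is likely to be small, bears on efficiency rather than bias, and does not touch the primary analysis or secondary endpoints 1 to 5.

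On OS, the protocol and SAP should be reconciled and the combined hazard ratio should be a commitment. The documents do not show that combined OS ought to replace the group-specific endpoints. That choice turns on whether the effect is shared across mutation groups, and every OS rate and hazard ratio used here is an assumption.

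**What to change.** 1. In SAP Section 8.3, state that every Cox model combining Mutation A and B in the FAP, including 5-year OS, is stratified by location, stage and mutation type, and that the combined tumour-site rows are stratified by stage and mutation type. Use the mutation status that Section 4.9.6 already prefers for analysis. Exempt the Table 10 row comparing ASA in Mutation A with placebo in A + B: its Mutation B strata would hold placebo subjects only and add nothing to the estimate. If the 3-year combined models have already been run, add the fuller stratification as a labelled addition.
2. State whether secondary OS is by group, combined or both, give the reason, and align the protocol's objective and analysis sentences with the SAP.
3. Move combined 5-year OS from optional to committed reporting: hazard ratio with 95% CI beside the two group-specific results. Its status need not change.
4. Label any change of endpoint status made after the 3-year unblinding as such, with its date.

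The cost is SAP and protocol wording. SAP Section 5.1 makes the OS analysis possible only from 19 August 2026. Ten strata instead of five leave 600/10 = 60 subjects per stratum on average, so little information is lost.
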